## **10. PHARMACODYNAMICS (EFFICACY)**

All PD summary tables, figures and listings will be based on the ITT Population. All analysis will be done by study part (SD/MAD) by each treatment group.

As a sensitivity analysis, the analysis will be repeated based on the PP population.

### **10.1 Definition of variables**

The following biomarkers will be analyzed:

- Procalcitonin;
- pGSN;
- TNF $\alpha$ ;
- TGF $\beta$ ;
- IL1 $\beta$ ;
- IL1ra;
- IL2;
- IL4;
- IL6;
- IL10;
- IL17a.

### **10.2 Biostatistical methods**

Biomarker will be summarized via counts and percentages of subjects for categorical variables, and by summary statistics for baseline, each observed time point, and ratio from baseline at each observed time point for continuous variables (as for the PK analysis with the exception of CV% and Geometric CV%) by treatment group and overall.

## 11. SAFETY

Safety endpoints will be analyzed using the Safety Population. All information will be presented by study part, for each treatment group and overall.

### 11.1 Adverse Events

#### 11.1.1 Definition of variables

- Adverse event (AE)
- Serious adverse event (SAE)
- Treatment emergent adverse event (TEAE)

AEs and SAEs are defined in the study protocol. TEAEs are defined as adverse events that occurred or worsened following the first administration of study medication. Adverse events that have missing onset dates will be considered treatment-emergent, unless the stop date is known to be prior to the first administration of the study medication.

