5.2. Endpoints

5.2.1. Primary Endpoint

- Incidence, causality, and severity of AEs and SAEs graded according to the National Cancer Institute (NCI) Common Terminology Criteria for Adverse Events (CTCAE) version 4.03 (or equivalent), clinically significant laboratory and/or electrocardiogram (EKG) abnormalities, death irrespective of cause, cause of death per investigator, including relationship to study drug; use of vasopressors, intubation, or transfer to the ICU or equivalent through Day 7

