5.2.2. Secondary Endpoints

- PK for rhu-pGSN including, but not limited to maximum concentration (C_{max}), time to maximum concentration (T_{max}), terminal half-life ($T_{1/2}$), area under the curve from time zero to 8 hours (AUC_{0-8}), area under the curve from time zero to infinity (AUC_{inf}) (levels measured within 30 minutes predose, 5-10 minutes after the end of administration, and 2, 8, 12 and/or 16, and 24 hours (\pm 30 minutes) after each dose (Day 3 sampling in multiple-dose arms is optional)

- Incidence, causality, and severity of AEs and SAEs graded according to the NCI CTCAE version 4.03 (or equivalent); clinically significant laboratory and/or EKG abnormalities as required by SOC; death irrespective of cause; cause of death per investigator, including relationship to study drug; use of vasopressors, intubation, or transfer to the ICU or equivalent through Day 28 (secondary time point)

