6.4. Data and Safety Monitoring Board

An DSMB will be established to monitor safety of subjects. The DSMB will be comprised of 3 members: a representative of the Contract Research Organization (CRO), a representative of the Sponsor, and an independent expert in CAP.

Safety through Day 7 of the study will be evaluated after the completion of each dosing arm to determine if it is safe to initiate the next cohort according to the safety criteria for stopping doses (Section 6.5).

Further details will be included in the DSMB charter.

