10.7. Reporting Adverse Events

All AEs, serious and nonserious, will be fully documented on the appropriate eCRF. For each AE, the Investigator must provide its duration (start and end dates or ongoing), intensity, assessment of causality and whether specific action or therapy was required.

All AEs that occur from the signing of the informed consent form (ICF) until the first dose of study drug should be recorded on the AE eCRF page only if the event was related to a study procedure. All other AEs/findings prior to first dose of study drug should be recorded as medical history on the applicable eCRF page. All AEs occurring from the first dose of study drug until 28 days after the last dose of study drug must be recorded on the AE eCRF.

All SAEs (related and unrelated) must be reported to the Sponsor within 24 hours of the Investigator's knowledge. This should be done by faxing/emailing the completed SAE Report Form to the number provided on the SAE Report Form. After the EOS Visit, only new treatment-related SAEs need to be captured on the AE eCRF and reported to the Sponsor.

Investigators must follow subjects with AEs/SAEs until the event has resolved, the condition has stabilized, withdrawal of consent, the subject is lost to follow up or death OR until the EOS Visit, whichever occurs first. New and ongoing treatment-related SAEs should be followed beyond the EOS Visit. If the subject dies, this should be captured as the outcome of the AE unless no link between the AE and the subject death can be established, in which case the AE will be marked as ongoing and the death will be reported as a separate event.

If a subject is lost to follow up, this should be captured accordingly within the AE eCRF and on the follow up SAE report.

The Sponsor or designee is responsible for notifying the relevant regulatory authorities of applicable suspected unexpected serious adverse reactions (SUSARs) as individual notifications or through periodic line listings. It is the Principal Investigator's responsibility to notify the Institutional Review Board (IRB) or IEC of all SAEs that occur at his or her site. Investigators will also be notified of all unexpected, serious, drug-related events (7/15 Day Safety Reports) that occur during the clinical trial. Each site is responsible for notifying its IRB or IEC of these additional SAEs.

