###### ***4.1.4 Per Protocol (PP) population***

The PP population will comprise all subjects in the safety population excluding subjects who missed doses and/or randomly discontinued the study before the primary Day 7 Visit. Furthermore, subject that had any relevant important protocol deviations will be excluded from the PP population.

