#### 11.1.2 Biostatistical methods

All AEs will be coded using MedDRA.

All AE summaries will be restricted to TEAEs only. Summary tables will include the number of subjects (%) experiencing an event and the number of events. Subjects will be counted only once at each system organ class (SOC) and preferred term (PT) level of summary.

The TEAE summaries will include:

- TEAE summary by SOC and PT
- TEAE summary of serious events by SOC and PT
- TEAE summary of deaths by SOC and PT
- TEAE summary by severity (NCI-CTCAE) by SOC and PT
- TEAE summary by causality to Study Drug by SOC and PT
- TEAE summary by causality to Study Procedure by SOC and PT
- TEAE summary of events leading to treatment discontinuation (Drug withdrawn) by SOC and PT

All AEs will be listed and will include verbatim term, PT, SOC, treatment, severity, causality, seriousness, and action taken with regards to the study drug. Separate listings will be created for SAEs, deaths and events leading to treatment discontinuation (Drug withdrawn).

Overall survival (time to death in days) will be analyzed through Kaplan-Meier methods and censored at the time of the study exit visit. Date of death will be taken as the SAE end date for which the outcome is stated to be fatal. Overall survival (days) = Date of event outcome of death/ Date of study exit - Date of first study drug administration + 1.

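### The primary safety endpoint runs through Day 7, but the SAP's adverse event, ICU, intubation and vasopressor summaries have no Day 7 cut

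*SAP*

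**What the plan says.** **Protocol.** Section 5.2.1 lists AEs and SAEs with causality and severity, deaths, and then "use of vasopressors, intubation, or transfer to the ICU or equivalent through Day 7" as the primary endpoint. Section 5.2.2 repeats essentially the same list as secondary, "through Day 28 (secondary time point". Section 10.7 requires that AEs "from the first dose of study drug until 28 days after the last dose of study drug must be recorded", and adds: "After the EOS Visit, only new treatment-related SAEs need to be captured on the AE eCRF and reported to the Sponsor".

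**SAP.** Section 4.1.4 treats Day 7 as the primary visit when it excludes from the per-protocol set subjects who "randomly discontinued the study before the primary Day 7 Visit". The safety analysis sets no such limit. Section 11.1.1 says: "TEAEs are defined as adverse events that occurred or worsened following the first administration of study medication". Section 11.1.2 says: "All AE summaries will be restricted to TEAEs only". No end day is given in the text, in the Section 17 titles or in the mock shells.

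The other items are handled as follows:
- **Deaths:** n (%) over the whole study and quartiles of survival time (Tables 14.3.3.9.1/.2). Kaplan-Meier plots (Section 19) and product-limit output (Sections 3 and 20) are also planned.
- **ICU and intubation:** whole-study counts and time to cessation (Section 11.8, Tables 14.3.4.13.1/.2).
- **Vasopressors:** a yes/no column in Listings 16.2.14.1/.2, and whatever appears in the concomitant medication counts of Section 11.7, which have no window.

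Section 15 declares no change from the planned analysis.

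**The concern.** The protocol separates its primary and secondary safety endpoints by time window alone. An analysis that ignores the window reports neither. Followed exactly, the SAP gives one set of AE tables running past Day 28, from which a reader cannot tell how many subjects had an event by Day 7.

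The study is descriptive, so these counts are the primary result. Under SAP Section 1, analyses not in the plan must be identified as unplanned in the study report. Day 7 tables added later would carry that label although they present the protocol's primary endpoint.

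**Working it through.** No figure in the plan belongs to this point, so the check compares planned outputs with the endpoint list and then sizes the window.

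**1. Planned tables against the endpoint list (SAP Section 17 and mock shells)**

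| Item | Tables | Cut at Day 7? |
|---|---|---|
| AEs: overall, SOC/PT, serious, grade, drug causality | 14.3.3.1, .2, .4 and .5 (each .1/.2), plus 14.3.1.6.1 and 14.3.3.6.2: 5 types × 2 study parts = 10 | No |
| Fatal AEs | 14.3.3.3.1/.2: 2 | No |
| Survival | 14.3.3.9.1/.2: 2 | Not in the tables; readable from plots and product-limit output |
| ICU, intubation | 14.3.4.13.1/.2: 2 | No |
| Vasopressors | No dedicated table | No |

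Total: 10 + 2 + 2 + 2 = 16 tables, of which 0 are cut at Day 7. A programming note on Table 14.3.4.13.2 asks for every scheduled time point. The shell it repeats has no time-point rows, so the note yields no Day 7 incidence.

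**2. Length of the period that is pooled in**

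With first dose as Day 1, recording to 28 days after the last dose ends nominally at:
- Single-dose part (last dose Day 1): 1 + 28 = Day 29.
- Multiple-dose part (last dose Day 3): 3 + 28 = Day 31.

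The end-of-study visit is Day 28 ± 4 (Protocol Tables 5 and 6). If routine capture stops there, the end lies between 28 − 4 = Day 24 and 28 + 4 = Day 32.

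Days after Day 7: 29 − 7 = 22 and 31 − 7 = 24 nominally; 24 − 7 = 17 to 32 − 7 = 25 if capture ends at that visit. Day 7 is therefore 7/29 = 24% or 7/31 = 23% of nominal recording days (range 7/32 = 22% to 7/24 = 29%). These are calendar fractions, not shares of events.

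**3. Effect of one subject whose only event of a type starts after Day 7**
- A dose level (n = 6): 1/6 = 16.7 percentage points.
- Placebo, if all are pooled as Protocol 11.1 and one sentence of SAP Section 3 say (n = 8): 1/8 = 12.5 points.
- Placebo by study part, as the SAP Section 3 group list and the shells show: 1/2 = 50 points (single-dose) and 1/6 = 16.7 points (multiple-dose).

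**4. The day count needed for a cut**

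The protocol synopsis and Section 6.2 make the day of admission Day 1 for analysis. Sections 6.1 and 6.3 and the footnotes to Tables 5 and 6 count from first dose, which may come up to 36 hours after presentation. Section 6.1 also calls the visit 7 days after starting therapy Day 7. If the first dose is Day 1, that is 1 + 7 = Day 8. The ± 1 day visit window absorbs this; a cut by date does not.

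**The case against.** **The phrase on Day 7 may govern only the last item of the list.** The parallel Day 28 wording in Section 5.2.2 and the term primary visit point to the whole list. Even on the narrow reading, vasopressor use, intubation and ICU transfer have no Day 7 summary.

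**Day 7 safety is already reviewed.** Protocol 6.4 says: "Safety through Day 7 of the study will be evaluated after the completion of each dosing arm". That stands for dose escalation, and a reader should not infer that escalation is compromised. The review decides whether the next cohort opens; it is not a final-analysis output.

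**The information can be recovered.** Much of it can. AE listings carry dates, and the planned survival outputs give Day 7 survival directly. A reader might infer that the Day 7 data are lost or that deaths cannot be assessed at Day 7; the documents support neither. Recovery is less sure for ICU and intubation, because the hospitalization listing shells show yes/no and a number of days without start dates. For vasopressors, Protocol 8.9 asks for medication start dates only if known.

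**An onset-date filter is not enough.** This is correct and shapes the fix. SAP 11.1.2 dates death by the end date of the fatal SAE, so a fatal event starting on Day 6 with death on Day 15 would wrongly become a Day 7 death. The AE listing shell shows one severity per event, so an event starting on Day 5 that reaches Grade 4 on Day 12 could appear as Grade 4 by Day 7.

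**The size is easily overstated.** Also correct. The 50-point figure holds only if single-dose placebo is shown alone, and the plan states both pooled and separate placebo. The day fractions say nothing about when events occur.

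**Conclusion.** The SAP does not report the protocol's primary safety endpoint for its own window, and it does not fix the secondary Day 28 window either. This should be corrected before the final analysis. Planned survival output partly covers deaths; AEs and SAEs, grade, causality, ICU transfer, intubation and vasopressor use are not covered.

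Nominally 22 to 24 days after Day 7 are pooled in (17 to 25 if capture ends at the end-of-study visit). One late-onset subject moves a dose-level rate by 16.7 points. For placebo the shift is 12.5 points if pooled, or 50 and 16.7 points if shown by study part. The documents give no event rates, so the share of events falling after Day 7 is unknown.

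The conclusion assumes that the Day 7 limit applies to the whole endpoint list; the ICU, intubation and vasopressor part does not depend on that. The day arithmetic takes the first dose as Day 1. No hypothesis test is planned for these outcomes, so no test result changes.

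**What to change.** In SAP 11.1.2 and Section 17:
- Produce the overall, SOC/PT, serious, grade and drug-causality tables through Day 7 (primary) and through Day 28 (secondary), and list later events.
- Assign AEs by onset date. State how an event that worsens after Day 7 is graded in the Day 7 table, and where events with a missing onset date go, since 11.1.1 generally keeps them as treatment-emergent.
- Count deaths through Day 7 and Day 28 by date of death as 11.1.2 defines it, with the same rule in every table.
- Add Day 7 and Day 28 n (%) rows for ICU transfer, intubation, vasopressor use and death to Tables 14.3.4.13.1/.2. First confirm that start dates for ICU stay, intubation and vasopressors are collected.
- State one study-day anchor and reconcile the protocol synopsis and Section 6.2 with Section 6.1 and the footnotes to Tables 5 and 6.
- Record the change in Section 15.

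**Cost.** If the existing versions become the Day 28 tables, this adds 5 types × 2 study parts = 10 tables, plus the two death tables re-cut by date of death. The hospitalization tables gain 4 items × 2 time points = 8 rows each. The grading rule needs more than a date filter. The eCRF is not among the documents; if start dates were not collected, sites must be queried. With 6 active subjects per dose level, many Day 7 cells will be sparse.

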#### 11.1.2 Biostatistical methods

All AEs will be coded using MedDRA.

All AE summaries will be restricted to TEAEs only. Summary tables will include the number of subjects (%) experiencing an event and the number of events. Subjects will be counted only once at each system organ class (SOC) and preferred term (PT) level of summary.

The TEAE summaries will include:

- TEAE summary by SOC and PT
- TEAE summary of serious events by SOC and PT
- TEAE summary of deaths by SOC and PT
- TEAE summary by severity (NCI-CTCAE) by SOC and PT
- TEAE summary by causality to Study Drug by SOC and PT
- TEAE summary by causality to Study Procedure by SOC and PT
- TEAE summary of events leading to treatment discontinuation (Drug withdrawn) by SOC and PT

All AEs will be listed and will include verbatim term, PT, SOC, treatment, severity, causality, seriousness, and action taken with regards to the study drug. Separate listings will be created for SAEs, deaths and events leading to treatment discontinuation (Drug withdrawn).

Overall survival (time to death in days) will be analyzed through Kaplan-Meier methods and censored at the time of the study exit visit. Date of death will be taken as the SAE end date for which the outcome is stated to be fatal. Overall survival (days) = Date of event outcome of death/ Date of study exit - Date of first study drug administration + 1.

## **11.2 Safety Laboratory Assessments**

Blood samples will be collected at the time points specified in the Schedule of Events (refer to the Protocol) to conduct Complete blood count (CBC), Coagulation and Comprehensive Metabolic Profile analyses.

### **11.2.1 Definition of variables**

The following tests will be performed within each of the specified test panels:

Complete blood count (CBC):

- Hematocrit (HCT);
- Hemoglobin (HGB);
- Red Blood Cells (RBC)
- White Blood Cells (WBC) with differential (including Eosinophils (EOS), Neutrophils (NEUT), Basophils (BASO), Lymphocytes (LYM) and Monocytes (MONO));
- Platelets (PLAT);
- Reticulocyte count

Coagulation:

- Prothrombin Time (PT) / International Normalized Ratio (INR);
- Partial Thromboplastin Time (PTT).

Comprehensive Metabolic Profile:

- Albumin (ALB)
- Blood Urea Nitrogen (BUN)
- Creatinine (CREAT)
- C-Reactive Protein (CRP)
- Lactate Dehydrogenase (LDH)
- Creatine phosphokinase (CPK)
- Alanine Aminotransferase (ALT)
- Aspartate Aminotransferase (AST)
- Total Bilirubin (BILI)
- Alkaline Phosphatase (ALP)
- Amylase
- Lipase

### **11.2.2 Biostatistical Methods**

All laboratory data collected at scheduled and unscheduled visits will be included in the listings, but only results collected as scheduled visits will be included in the summary tables.

Results for individual parameters may be reported in different units depending on the analyzing laboratory. If required, the results (and the corresponding normal range cut-off values) for individual parameters may be converted to International System of Units (S.I.) units to summarize the data.

For the all parameters where a unit value has been reported, the parameter names that will be used in the outputs will comprise of the test name and the unit of measure, for example, 'Albumin (g/L)'. Parameters will be sorted alphabetically within tables and listings.

For all parameters where a normal range limit value is reported, the normal range will be derived based on the available lower and upper limit values and any reported mathematical symbols. If both a lower and upper limit value is available, the normal range will be presented as '(Lower, Upper)'.

The reported results for each parameter with a defined normal range will be classified ('Low', 'Normal', 'High') in relation to the defined normal range limits. If a result is equal to the normal range cut-off value, the result will be considered 'Normal'.

The change from baseline values at each post-baseline visit will be calculated for all parameters with continuous results (except for specific gravity and pH).

The decimal precision for each parameter will be based on the maximum number of decimals to which the reported result or the normal range limits are presented to in the raw data. The results and normal ranges will be displayed to the same decimal precision in the listings.

If a result for a parameter that is normally considered continuous is reported as a range (i.e., the result for basophils is reported as '<0.01' for a single time point), the result may be converted to a numeric value that is smaller than the reported result to contribute to the derivations and the summary statistics. Any conversion rules that are applied will be highlighted in the footnotes of the affected tables and listings. The original reported result value will however be included in the listing.

The laboratory result tables will present summary statistics for each laboratory parameter within the specific test panel. For each parameter, summaries will be presented for the baseline and each scheduled post-baseline visit. In addition, summaries will be presented for the change from baseline values at each scheduled post-baseline visit.

Additionally, counts (%) of number subjects with values out of normal range at each scheduled time point will also be presented along with shift tables that will represent the changes in normal range categories across post-baseline time points.

The listings of laboratory parameters will include all the information (fields) collected. In addition, the observations that are used as the baseline record (value) for each parameter will be flagged, and the change from baseline values at each post-baseline visit will be presented.

For all parameters, standardized values will be reported.

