11.3. Analysis Populations

No data will be excluded from the summary statistics and analyses, and missing data will not be imputed. AEs, including death, will be carried forward. As a sensitivity analysis to the intention-to-treat population, a per-protocol population excluding subjects who missed doses and/or randomly discontinued the study before the primary Day-7 Visit will be analyzed.

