- Repeat assessments (Safety): No repeat assessments will be included in summary presentations (Tables, Figures). Only the original values will be used in summary presentations. All repeat assessments captured in the Electronic Data Capture (EDC) system will be presented in the data listings.
- Assessment windows: All assessments will be included in the data listings and no visit windows will be applied to exclude assessments that were performed outside of the protocol specified procedure windows.
- Date and time display conventions: The following display conventions will be applied in all outputs where dates and/or times are displayed:
  - o Date only: DDMMMYYYY
  - o Date and time: DDMMMYYYY /HH:MM

If only partial information is available, unknown components of the date or time will be presented as 'NK' (not known), i.e., '2016-NK-NK'. Times will be reported in military time.

In the summary tables and figures, treatment groups will be summarized separately for SD/MAD, each cohort, combined placebo and overall (all subjects). Study outcomes will be summarized as follows:

- For each active dose level (overall):
  - o SD Phase:
    - rhu-pGSN 6 mg/kg
    - Placebo
    - Overall
  - o MAD Phase
    - rhu-pGSN 6 mg/kg
    - rhu-pGSN 12 mg/kg
    - rhu-pGSN 24 mg/kg
    - Combined Active
    - Combined Placebo
    - Overall

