## GENERAL COMMENTS

- Where a count is 0, the percentage will not be shown (e.g. 0 (0.0%)) will be displayed as 0)
- Unless otherwise stated, parameters will be listed in alphabetical order
- Percentages and their 95% CI, where appropriate, will be presented to one decimal place
- The minimum and maximum values will be presented to the same number of decimal places as recorded in the electronic Case Report Form (eCRF)
- Mean, median, and SD will be presented to one more decimal place than the raw data
- Percentages will be rounded to one decimal place, with the denominator being the number of subjects in the relevant population with non-missing data, unless otherwise specified
- Change from Baseline:  
Change from Baseline will be calculated as:  
$$\text{Change from baseline} = \text{new value} - \text{baseline value}$$
- Unscheduled visits will be excluded from summary tables
- Names and order of Treatment Groups

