**Programming Note:**  
 Include all CBC Parameters and all scheduled time points.

Clinical cut-off date: DDMMYYYY  
 Program: filepath\_name, Output: filepath\_name (version x.x) Created: DDMMYYYY HH:MM

Table 14.3.4.1.1.2 MAD: Summary of CBC (Summary of Actual and Change from Baseline Values) by Timepoint  
Protocol: BTI-201  
Safety Population

Clinical cut-off date: DDMMYYYY  
Program: filepath\_name, Output: filepath\_name (version x.x) Created: DDMMYYYY HH:MM

Programming Note:  
Repeat Table 14.3.4.1.1.1  
Include all CBC Parameters and all scheduled time points.  
  
Include: rhu-pGSN 6 mg/kg;  
          rhu-pGSN 12 mg/kg;  
          rhu-pGSN 24 mg/kg;  
          Combined Active;  
          Combined Placebo;  
          Overall

Table 14.3.4.1.2.1 SD: Summary of CBC Shifts from Baseline (Low, Normal, High)  
 Protocol: BTI-201  
 Safety Population

		Baseline 					
Parameter	Result Classification	Low n (%)	Normal n (%)	High n (%)	Missing n (%)	Total n (%)	
Hemoglobin (g/L)	Day 2						
	Low	xx (xx.x%)	xx (xx.x%)	xx (xx.x%)	xx (xx.x%)	xx (xx.x%)	
	Normal	xx (xx.x%)	xx (xx.x%)	xx (xx.x%)	xx (xx.x%)	xx (xx.x%)	
	High	xx (xx.x%)	xx (xx.x%)	xx (xx.x%)	xx (xx.x%)	xx (xx.x%)	
	Missing	xx (xx.x%)	xx (xx.x%)	xx (xx.x%)	xx (xx.x%)	xx (xx.x%)	
	Total	xx (xx.x%)	xx (xx.x%)	xx (xx.x%)	xx (xx.x%)	xx (xx.x%)	
	Day 3 or 4						
	Low	xx (xx.x%)	xx (xx.x%)	xx (xx.x%)	xx (xx.x%)	xx (xx.x%)	
	Normal	xx (xx.x%)	xx (xx.x%)	xx (xx.x%)	xx (xx.x%)	xx (xx.x%)	
	High	xx (xx.x%)	xx (xx.x%)	xx (xx.x%)	xx (xx.x%)	xx (xx.x%)	
	Missing	xx (xx.x%)	xx (xx.x%)	xx (xx.x%)	xx (xx.x%)	xx (xx.x%)	
Total	xx (xx.x%)	xx (xx.x%)	xx (xx.x%)	xx (xx.x%)	xx (xx.x%)		

rhu-pGSN: 6 mg/kg  
(N=xx)

etc. etc.

Note Baseline is defined as the last valid, non-missing assessment prior to first study drug administration. Unscheduled visits not included in post baseline assessments.

Programming Note:  
 Also Include: Placebo, Overall  
 Include all CBC Parameters and all scheduled time points.

Clinical cut-off date: DDDMMYYYY  
 Program: filepath\_name, Output: filepath\_name (version x.x) Created: DDDMMYYYY HH:MM

Table 14.3.4.1.2.2 MAD: Summary of CBC Shifts from Baseline (Low, Normal, High)  
Protocol: BTI-201  
Safety Population

Clinical cut-off date: DDMMYYYY  
Program: filepath\_name, Output: filepath\_name (version x.x) Created: DDMMYYYY HH:MM

Programming Note:  
Repeat Table 14.3.4.1.2.1  
Include all CBC Parameters and all scheduled time points.  
  

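### Out-of-range laboratory values seen only at an unscheduled draw, or only at a worse repeat, reach no laboratory table by dose, and the SAP does not declare this as a change from the protocol

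*SAP*

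**What the plan says.** Several places in the SAP restrict what enters the laboratory tables.

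- SAP 11.2.2 sends scheduled and unscheduled results to the listings, but "only results collected as scheduled visits will be included in the summary tables".
- The same section plans "counts (%) of number subjects with values out of normal range at each scheduled time point", together with shift tables across the post-baseline time points.
- The general comments before the mock tables say "Unscheduled visits will be excluded from summary tables". The footnote to the CBC, coagulation and metabolic shift shells (Tables 14.3.4.1.2.1, 14.3.4.2.2.1 and 14.3.4.3.2.1) reads "Unscheduled visits not included in post baseline assessments".
- SAP section 3 removes repeat safety assessments from tables and figures: "Only the original values will be used in summary presentations".

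The protocol is worded differently. Section 11.3 says "No data will be excluded from the summary statistics and analyses". Section 11.4.1 asks for counts below, within and above the normal range, and for summary statistics at baseline and at every observed time point. It does not limit these to scheduled visits. SAP section 15, which is the place for departures from the planned analysis, reports none.

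**The concern.** The subjects are inpatients with pneumonia, so laboratory tests outside the schedule are expected. The protocol synopsis provides for repeat laboratory work during the admission when standard of care calls for it. Protocol 10.6 requires clinically significant abnormalities to be followed until they return to baseline levels or fit the subject's condition. Draws of this kind are often made because something has changed, and they are the ones the tables leave out.

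At stake is the reader's ability to see, by dose, how many subjects ever went out of range on a parameter. The tables meant to show laboratory abnormality cannot answer that. A zero in them may mean that no subject was abnormal, or that the abnormality was found on a day without a scheduled draw.

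**Working it through.** This is a data-handling rule and not a stated calculation, so the check is mainly a comparison of texts, followed by a small illustration.

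**1. Do the texts conflict?** Protocol 11.3 excludes no data and Protocol 11.4.1 summarizes observed time points. SAP 11.2.2, SAP section 3 and the mock-table rules exclude unscheduled and repeat results. SAP section 15 declares nothing. The SAP is narrower than the protocol and does not say so.

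**2. What is lost?** Take a MAD subject whose parameter is normal at baseline. As far as the layout of protocol Table 6 can be read, the scheduled post-baseline laboratory draws through Day 7 are on Days 2, 4 and 7. Suppose all three are normal and an unscheduled Day 5 draw is high.
- Shift table: Normal-to-Normal at each visit.
- Out-of-range count: not counted at any visit.
- Listings: the value appears with a High flag and a clinical-significance flag (Listings 16.2.8.x).
- Adverse events: counted only if the investigator judges it clinically significant or it is treated (Protocol 9.2.6 and 10.6; SAP 11.1.2).

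**3. What about repeats?** The original value is kept. If an abnormal result prompts a re-check, the abnormal value stays in the table. Something is lost only when the repeat is worse than the original.

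**4. Would lifting the exclusion be enough?** No. All the tables are by visit. If the scheduled counts are 1/6 on Day 2 and 1/6 on Day 7, the number of subjects ever out of range is 1 or 2, and the tables cannot say which. An any-time row is needed as well.

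**5. Is there another laboratory count?** Vital signs and EKG have tables of investigator interpretation that count clinically significant findings (Tables 14.3.4.5 and 14.3.4.7). Laboratory results have none; their significance flags appear only in listings.

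**6. Illustration of size.** The input is 6 active subjects per dose cohort (Protocol 6.1). The nearest figure in the plan is the zero-event rate for n = 6 in protocol Table 7 (SAP Table 1), given as 32%. It reproduces: 1 − 0.10^(1/6) = 31.9%. The plan applies it to adverse events and it is borrowed here for scale.
- One subject counted: 1/6 = 16.7%. The exact one-sided 90% upper bound solves (1 − p)^6 + 6p(1 − p)^5 = 0.10, which gives p = 51.0%.
- The same subject not counted: 0/6 = 0%, upper bound 31.9%.

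**7. How often might it happen?** The documents give no number of unscheduled draws. Assume u extra draws beside 3 scheduled ones through Day 7, with the worst value equally likely at any draw. The worst value then falls outside the tables with probability u/(3 + u):

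| u | Probability |
|---|---|
| 1 | 25% |
| 2 | 40% |
| 3 | 50% |
| 4 | 57% |

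Draws prompted by deterioration would raise these shares. On the other hand, the subject's out-of-range status is lost only if no scheduled value was out of range in the same direction. The table shows a range under an assumption and is not an estimate for this trial.

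**The case against.** The strongest reply is that little of clinical importance escapes. Results judged clinically significant or treated must be reported as adverse events whichever draw they came from, and treatment-emergent events are counted by subject. All results are listed, abnormal ones in separate flagged listings. With 32 subjects, those can be read line by line. This stands, and it limits the point. What it leaves open is a count by dose: the adverse-event route depends on investigator judgement, and Protocol 10.6 prefers a syndrome term, so the event may not be identifiable as a laboratory finding.

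The protocol conflict can also be read more softly. The no-exclusion sentence sits under analysis populations and could be about subjects, and Protocol 11.1 leaves further detail to the SAP. However, the sentence says data, and the laboratory section separately refers to observed time points. A declaration is still owed.

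A reader might infer three stronger things that the documents do not support.
- *The worst values in these patients go uncounted.* Worst values at scheduled visits are counted, and so is an abnormal original that prompted a repeat.
- *The primary endpoint is understated.* That endpoint concerns clinically significant abnormalities, which should reach the adverse-event tables. The shift tables show only Low, Normal or High and do not measure severity.
- *About half of the days through Day 7 are missed.* Days 3, 5 and 6 appear to have no scheduled MAD draw, but that describes the sampling schedule. If no blood was taken, no table rule can recover the value; if it was taken, it is listed.

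Finally, more draws mean more chances of an out-of-range value, so an any-time count partly reflects how often a subject was sampled. That is a fair drawback of the remedy.

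**Conclusion.** The point holds in a limited form. The SAP keeps unscheduled and repeat laboratory results out of all laboratory summary, out-of-range and shift tables. This is narrower than the protocol's wording and is not declared. No planned table gives an any-time count of laboratory abnormality by dose. The affected values are those seen only at an unscheduled draw, or only at a repeat worse than the original; they remain in the listings and, where significant or treated, should appear as adverse events.

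The size cannot be derived from the documents. One affected subject moves a six-subject dose group by 16.7 percentage points on that parameter, provided that subject had no scheduled value out of range in the same direction. The by-visit tables remain valid for what they describe, and restricting by-visit means to scheduled draws is sound practice. The change is worth making because the data are already collected and the gap concerns safety tables in very small groups.

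**What to change.** 1. Keep the by-visit summaries on scheduled results.
2. Add worst-post-baseline rows to each laboratory shift and out-of-range table, one set through Day 7 and one through Day 28. Show the lowest and the highest category reached, since a subject can go both ways. Use all scheduled, unscheduled and repeat results except those the laboratory voided, and count each subject once per direction.
3. Amend SAP section 3, SAP 11.2.2 and the mock-table comments and footnotes so that their exclusions apply to the by-visit rows only.
4. Declare the by-visit restriction in SAP section 15 as a departure from Protocol 11.3 and 11.4.1.
5. Footnote the number of laboratory draws per group on the new rows, so that unequal sampling is visible.

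The cost is a little programming, with no new data. The remaining drawback is the dependence on sampling frequency, which the footnote discloses but does not remove.
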